## List of Abbreviations

AE	Adverse Event
ANOVA	Analysis of Variance
ANCOVA	Analysis of Covariance
BALP	Bone specific alkaline phosphatase
BMD	Bone mineral density
BTM	Bone turnover marker
Ca.	Calcium
CRD	Clinically Relevant Difference
CRF	Case Report Form
cOC	Carboxylated Osteocalcin
CTCAE	Common Toxicity Criteria
CTX-1	Cross-linked C-telopeptide type I collagen
DXA	Bone Densitometry by X Ray
DHNA	1,4- Dihydroxy naphthoic Acid
DM	Data Management
FSH	Follicle stimulating hormone
GCP	Good Clinical Practice
GP	General Practitioner
ID	Identification
IEC	Independent Ethical XCS Committee
LH	Luteinising hormone
MR	Meddoc Research
MS	Muscle Strength
NMBU	Norges Miljø- og Biovitenskaplige Universitet
OED	Optimal Efficacy Dose
OP	Osteopeni
R 0	Osteocalcin ratio
PI	Principal Investigator
PINP	Procollagen type 1 N-terminal propeptide
PTH	Parathyroid hormone
QoL	Quality of Life
RSP	Response Surface Pathway design
SAE	Serious Adverse Event
SAS	Statistical Analysis Systems
SD	Standard Deviation
SHBG	Sexual hormone binding globulin
SOP	Standard Operating Procedure
OUH	Oslo University Hospital
ucOC	Under carboxylated Osteocalcin
UIO	University of Oslo

## I: Synopsis

**1.1: Title:** The effect on bone marker and body mineral density (BMD) of daily Jarlsberg Cheese intake in risk patient for Osteoporosis.

### 1.2: Protocol number:

Protocol identification: PR-Jarlsberg/III\_2022

Regional Ethical Committee number: 536927

EudraCT number: 2022-003252-13

ClinicalTrial.gov:

### 1.3: Aim

- To estimate the effect of daily optimal efficacy dose (OED) of Jarlsberg cheese on BMD and bone markers to patients with Osteopeni (OP).
- To compare daily intake of Calcium (Ca) and vitamin D with and without OED of Jarlsberg on BMD and bone markers to OP patients.
- To compare daily intake of Calcium (Ca) and vitamin D with and without OED of Jarlsberg on Time-to-Osteoporotic (TTO) treatment is recommended.

**1.4: Study population:** The study population consists of OP-patients of post-menopausal women and men above 50 years of age. OP patients are defined as patients with a T-score below 0.0 but larger than -2.5.

**1.5: Trial treatment:** The optimal daily intake of Jarlsberg cheese depending on gender, age, and physical activity.

Women in menopausal age have a daily OED Jarlsberg of 57 gram and men in the same age interval have an estimated OED of 65 gram.

Women in post-menopausal age have a daily OED Jarlsberg of **XX** gram and men in the same age interval have a daily OED of **YY** gram.

The cheese will be delivered in package of 250 gram with slices of 15.625gram. 57 gram represents 4 slices; 65 gram 4.5 slices; **XX** gram represents **xx** slices and **YY** represents **yy** slices. All the included patients will receive 20µg vitamin D and 1000 mg Ca. Half of the patients will receive vitamin D and Ca-tablets plus Jarlsberg cheese (Treatment group I) and other half only vitamin D and Ca-tablets (Treatment group II).

### 1.6: Design and randomization

#### 1.6.1 Design:

The study will be performed as a randomized, single-blinded Norwegian multicentre trial with stratified semi-cross-over design with gender and participating General Practitioner (GP) site as stratification factors. 10 GP's from Viken county will participate.

### 1.6.2 Randomization:

Patients included in the study will be allocated to one of the two treatment groups by block randomization with random block size between 2 and 6.

**1.7: Main variables:** The main response variable will be the change in Bone Mineral Density (BMD) and recorded at baseline and every 16 weeks. The second main variables will be total Osteocalcin (tOC), carboxylated osteocalcin (cOC), the osteocalcin ratio  $R_O$  defined as the ratio between cOC and under-carboxylated osteocalcin (ucOC) [ $R_O = cOC / ucOC$ ] and measured at start, week 4, week 16, week 20, week 32 and week 48. Additionally, the bone markers cross-linked C-telopeptide type I collagen (CTX), procollagen type 1 N-terminal propeptide (PINP), bone specific ALP (BALB) and Parathyroid hormone (PTH) will be measured at the same visits. At baseline and every 16 weeks, the following variables will be measured: Vitamin K2 and the different vitamers MK-7, MK-8, MK-9, and MK-9(4H) used as explanatory variable; Diet registration as controlling variables and HbA1C, Lipids, biochemical variables together with “Quality-of-Life” (QoL) questionnaire as supporting variables. The Interleukins IL-1 $\beta$ , IL6, IL8, IL10 and the Cytokines TNF- $\alpha$ , NF- $\kappa$ B (RANK-L), OPG and TGF- $\beta$  will be measured initially and at the last visit in the study. The Common Terminology Criteria for Adverse Events version 4.0 (CTCAE) will be used for registration of Adverse Events (AE) and toxicity score at every investigation visit.

## 1.8: Study procedure

### 1.8.1 Screening and baseline

Participants, who fulfil the inclusion criteria, do not meet any of the exclusion criteria and willing to give informed consent to participate will be included in a screening period of one week. During this screening week, all the possible participants will receive 40 $\mu$ g vitamin D and 500 mg Ca tablets per day but asked not to eat Jarlsberg cheese.

DXA with BMD measurements will be taken at the start of the screening week. Patients with a BMD T-score  $\leq -1.0$  will be included in the study starting with baseline measurements (Day 0). All demographic data, social factors, history of disease and vital signs will be recorded at baseline. The participating patients will be given a Diet-App on the web or mobile phone for registration of the daily food intake during four first consecutively days after baseline. Blood samples for measurements of Osteocalcin, CTX-1, PINP, BALP, PTH and vitamin K will be taken fastening in the morning. Additionally, blood samples for measuring biochemical variables, HbA1C, Lipids, Interleukins and Cytokines, will be recorded. The Common Terminology Criteria for Adverse Events (CTCAE) version 4.0 used for measuring and classifying the tolerability and toxicity will be recorded as well. The patients will be given compliance & activity form and asked to write down the daily intake of treatment medicine, Jarlsberg cheese and hours of physical activities.

### 1.8.2 Clinical part

The patients will be allocated (1:1) to vitamin D + Ca-tablets  $\pm$  Jarlsberg cheese. All the participants will get new delivery of vitamin D and Ca-tablets every four weeks. The patients allocated to Jarlsberg will additionally receive Jarlsberg cheese. The patients will receive a compliance & activity form and asked to fill in every day. All the patients meet for new visits at week 4, week 16, and week 32. Patients allocated to only vitamin D + Ca tablets at baseline well additionally meet for visits at week 20 and week 48. At all these visits blood samples for

measurement of Osteocalcin, CTX-1, PINP, BALP and PTH will be drawn fasting in the morning, and concomitant medication and treatment compliance recorded. The main visits will be performed every 16 weeks. New DXA screening will be performed. Patients obtaining a BMD T-score  $\leq -2.5$  will discontinue the study and switched to antiresorptive treatment plus daily OED of Jarlsberg cheese. The daily food intake during four consecutively days will be recorded on the Diet-App. Blood samples for measurements of Osteocalcin, CTX-1, PINP, BALB and PTH will be drawn fastening in the morning at every visits. Furthermore, blood samples for measuring and biochemical variables, HbA1C and Lipids, will be recorded. The CTCAE will be recorded as well. The visit at Week 32 and Week 48 will be the last observation in the study for the patients initially allocated to Jarlsberg and controls, respectively. In addition to the mentioned variables blood samples for measurement of Interleukins and Cytokines will be performed. All the patients completed the study will be offered to continue the daily intake of Jarlsberg cheese. These patients will be followed up one year after the last visit with a new DXA and a blood sampling for measurements of the Osteocalcin level and the bone markers PINP, CTX and BALP.

**1.9: Sample size:** With a significance level of 5%, a power of 90% and a Clinically Relevant Difference (CRD) of one time the Standard Deviation in change of BMD, at least 24 patients in each group must finalize the study. With an expected drop-out rate of 25%, 30 patients in each group must be included.

### 1.10: Time schedule

A patient recruitment period of 12 months may be needed. The duration of each included patient will be between 32 and 48 weeks. The total duration of the study will be as follows:

Inclusion of the first patient	15-06-2023.
Inclusion of the last patient	15-06-2024.
The first patient finalized	15-01-2024.
The last patient finalized	15-12-2024.
Closing database	15-09-2025.
Finalized Clinical Study Report	15-10-2025.
Draft of manuscript for publication	15-12-2025.
One Year follow-up period	15.01.25 – 15.12.25.

## 1.11: Flow chart

ITEMS	Screening & Baseline	Weeks					Follow-Up +1 Year
		Comparison 4	16(0)	20 (4)	Switch 32(16)	48(32)	
Inclusion and Exclusion criteria	x						
Oral & written informed consent	x						
Patient factors	x						
History of disease	x						
Diet registration	x		x		x	x	
Physical exam.	x		x		x	x	x
DXA-screening	x		x		x	x	x
Concomitant medication	x	x	x	x	x	x	x
Treatment compliance 		x	x	x	x	x	x
Blood sampling							
- Total Osteocalcin (tOC)	x	x	x	x	x	x	x
- Carboxylated Osteocalcin (cOC)	x	x	x	x	x	x	x
- Under carbox. Osteocalcin (ucOC)	x	x	x	x	x	x	x
- Collagen1 (CTX-1)	x	x	x	x	x	x	x
- Procollagen 1 (PINP)	x	x	x	x	x	x	x
- Bone specific ALP	x	x	x	x	x	x	x
- Parathyroid hormone (PTH)	x	x	x	x	x	x	x
- Vitamin K 1	x		x		x	x	
- MK-7	x		x		x	x	
- MK-8	x		x		x	x	
- MK-9	x		x		x	x	
- MK-9(4H)	x		x		x	x	
- Vitamin D	x		x		x	x	x
- Haemoglobin	x						
- Ferritin	x						
- Creatinine	x		x		x	x	
- HbA 1c	x		x		x	x	x
- Ca, Mg, Albumin	x		x		x	x	x
- Urea, Phosphate	x		x		x	x	x
- LDL-cholesterol	x		x		x	x	x
- HDL-cholesterol	x		x		x	x	x
- Interleukins /cytokines	x				x	x	
- TSH & FT4	x				x	x	
Adverse Events [CTCAE]	x	x	x	x	x	x	
End of treatment					x	x	

**Red numbers** indicate only the visits after switching to Jarlsberg in the control group.

 Treatment compliance will be performed every four weeks.

## II: Introduction

### 2.1: Background

Bone loss remains a huge problem among the elderly. It is well established that dietary calcium and vitamin D are beneficial for skeletal health, but more recently research clearly demonstrates the importance of vitamin K and health claims stating the positive effects on the skeleton have been authorized by the European Food Safety Authority (EFSA). Dairy products are good calcium sources, important for bone formation. But cheese is also an important vitamin K, especially vitamin K2 source, indicating that cheese consumption may strengthen bones and reduce the risk of osteoporosis.

Recently, a Norwegian multicentre study comparing daily intake of Jarlsberg® and cheese without vitamin K2 has been performed. 66 healthy female volunteers (HV) were recruited. By skewed randomization (3:2), 41 HV were allocated to daily intake of 57 g Jarlsberg® (J-group) and 25 to 50 g Camembert (C-group) in 6 weeks. After 6 weeks the C-group was switched to Jarlsberg®. The study duration was 12 weeks with clinical investigations every six weeks. The main variables were procollagen type 1 N-terminal propeptide (PINP), tOC, carboxylated osteocalcin (cOC) and the osteocalcin ratio (RO) defined as the ratio between cOC and under-carboxylated osteocalcin. Serum cross-linked C-telopeptide type I collagen (CTX), vitamin K2, lipids and clinical chemistry were used as secondary variables.

The study found that PINP, tOC, cOC, RO and vitamin K2 increased significantly ( $p < 0.01$ ) after 6 weeks in the J-group. PINP remained unchanged in the C-group. The other variables decreased slightly in the C-group but increased significantly ( $p \leq 0.05$ ) after switching to Jarlsberg®. No CTX-changes detected in neither of the groups. Serum lipids increased slightly in both groups. Switching to Jarlsberg, total cholesterol and LDL-cholesterol were significantly reduced ( $p \leq 0.05$ ). HbA1c, Ca++ and Mg++ were significantly reduced in the J-group, but unchanged in the C-group. Switching to Jarlsberg, HbA1c and Ca++ decreased significantly.

The optimal efficacy daily dose (OED) of Jarlsberg® cheese used in this study has previously been estimated in a study on fertile women. A recently performed dose-response-study on post-menopausal female and male participants above the age of 50 estimated the OED of Jarlsberg cheese to be XX for women and YY for men. For participating fertile women in this new study, the Jarlsberg OED of 57 g/day estimated in the first dose-response study will be used. For the other included patients, the OED estimated in the last dose-response study will be used. Previously only tOC, cOC and the Bone Turnover Markers (BMT) as PINP, CTX and Bone specific Alkaline Phosphatase (BALP) were recorded. In this study Body Mineral (BMD) will be the main variable.

### 2.2: Osteocalcin and Vitamin K

Activated osteocalcin has a key role in bone formation and maintenance. It is one of the body's 17 so called GLA proteins, all of which being activated by carboxylation in a process involving vitamin K. While vitamin K dependent coagulation factors are practically fully carboxylated under normal conditions, osteocalcin is not. The ratio of fully carboxylated to under carboxylated osteocalcin in the blood (OR) reflects a person's vitamin K status. The high levels of under carboxylated osteocalcin in healthy people indicate that suboptimal vitamin K status or subclinical vitamin K deficiency is common in Western societies. Very low ORs have been associated with osteoporotic fractures.

Figure 1 shows the structure of common forms of vitamin K. Vitamin K1 is produced in plants and found at high concentrations in leafy vegetables and is the dominating variant in the Western diet.

[figure not shown]

Figure 1: Structures of some vitamin K variants

Vitamin K2 (menaquinone, MK) is found in several variants (Fig 1). The short-chained MK-4 can be formed from vitamin K1 in humans and is found in animal products like liver. The K2 vitamers with longer side chains, like MK-7, MK-8, MK-9 and MK-9(4H) are of bacterial origin. They can be found in certain fermented foods. In the Western diet fermented dairy products like cheese are the main source of vitamin K2.

The long chained MKs have been found to have greater extra-hepatic activity than K1 and MK-4, possibly due to more efficient uptake and much longer serum half-life. Prospective cohort studies have demonstrated health benefits that can be attributed the intake of vitamin K2 but not K1, and the main contributor to the vitamin K2 is cheese containing MKs with long side chains.

### 2.3: Jarlsberg Cheese

The dominating K2 vitamer is MK-9 in most cheeses, but the amount varies considerably. However, some cheeses also contain MK-9(4H). Jarlsberg cheese is rich in this compound. This cheese is made with lactic acid bacteria producing MK-8 and MK-9 and *Propionibacterium freudenreichii* (PF) producing MK-9(4H).

Table I: Typical vitamin K2 content of 100g Jarlsberg cheese

Component	
MK-8	3 µg
MK-9	13 µg
MK-9(4H)	75 µg

Although vitamin K2 related health benefits have been associated with cheese, the effects of cheese consumption on bone health have never been studied in intervention studies. Because of its high vitamin K2 content Jarlsberg cheese is well suited for such a study.

Recently, a dose-response studies in healthy Norwegian women was performed with a 3-level between patient Response Surface Pathway design. These studies showed a significant increase of OC and cOC. Jarlsberg Cheese has been compared to Camembert cheese which does not contain any vitamin K2, and no similar effects on the Osteocalcin level was detected after Camembert consumption.

**Table II: Nutritional content of 100g Jarlsberg® and Camembert Cheese**

Nutritional content	Jarlsberg cheese	Camembert cheese
Energy	1458 kJ	1359 kJ
Fat	27 g	28 g
Saturated fatty acids	17 g	18 g
Carbohydrate	0 g	0 g
Sugars	0 g	0 g
Protein	27 g	19 g
Salt	1.1 g	1.5 g
Vitamin A	270 µg (34%)	280 µg (35%)
Riboflavin	0.32 mg (23%)	0.33 mg (24%)
Folic Acid	36 µg (18%)	51 µg (26%)
Vitamin B12	2.2 µg (88%)	1.7 µg (67%)
Calcium	770 mg (96%)	540 mg (68%)
Phosphorus	550 mg (79%)	390 mg (56%)
Zinc	4.2 mg (42%)	3.0 mg (30%)
Selena	12 µg (22%)	11 µg (20%)
Iodine	32 µg (21%)	45 µg (30%)

The mainly used prophylactic treatment against osteoporosis is still the combination of dietary calcium and vitamin D. This combination is shown to be beneficial for skeletal health, but not sufficient. To what extent will daily OED consumption of Jarlsberg cheese affect this effect?

#### 2.4: Aims.

- To estimate the effect of daily optimal efficacy dose (OED) of Jarlsberg cheese on BMD and bone markers to patients with Borderline Osteoporosis (BO).
- To compare daily intake of Calcium (Ca) and vitamin D with and without OED of Jarlsberg on BMD and bone markers to BO patients.
- To compare daily intake of Calcium (Ca) and vitamin D with and without OED of Jarlsberg on Time-to-Osteoporotic (TTO) treatment is recommended.

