## IV: Design and randomization

### 4.1: Study design

The study is performed as an open randomized semi crossover design with two strata. Sex is used as a stratification factor (Figure 1). The two strata are chosen because of different OED of cheese for women and men. Within each stratum the participants will be allocated either to vitamin D + Calcium alone (Control) or with daily OED of Jarlsberg cheese (Jarlsberg). The two groups will run parallelly in 16 weeks and BMD recorded by DXA. Patient with T-score < -2.5 classifies as Osteoporotic patients will be withdrawn from the study. At week 16, the patients in the control-group will be switched to additional daily OED of Jarlsberg cheese for 32 weeks. The patients randomised to Jarlsberg will continue with the same treatment for additionally 16 weeks.

[figure not shown]

Figure 2: Study design with time schedule and variables to be recorded. Measurements given in red (x) is related only to the patients initially randomised to only vitamin D + Ca (control).

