## V: Evaluation

### 5.1: Bone mineral density (BMD)

DXA will be used as a surrogate measurement of BMD at baseline and every 16 weeks. BMD will be given in  $\text{gram}/\text{cm}^2$  and use for estimating changes in total BMD, BMD L1-L4 and left and right neck of hip. The participants will be weighed in their underwear, and height will be measured with a fixed stadiometer. A dual energy X-ray absorptiometry performing the three-site scan i) lumbar area [L2-L4], ii) femoral neck, trochanter, and shaft [proximal femur], and iii) whole body compares the bone density with the bone density expected for a healthy adult of the same age, gender, and ethnicity as the patient. The difference is calculated as a standard deviation (SD) score. The difference between the patient measurement and that of a young healthy adult is known as a T score. The T scores classifies as follows:

- above -1 SD is normal
- between -1 and -2.5 SD is defined as mildly reduced bone mineral density (BMD) compared with peak bone mass (PBM)
- below -2.5 SD is defined as osteoporosis

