#### 6.2.2: Comparative phase

All the participants meet for clinical investigations at week 4 and week 16 in the comparative phase of the study. At week 4, blood samples will be taken for measurements of Osteocalcin and the BTMs. Additionally, concomitant medication, adverse events (AE) and treatment compliance will be recorded. Cheese and vitamin D + Ca for the next 4 weeks will be delivered. A new delivery will be handed over by a representative from the Meddoc team at week 8 and week 12 in the study. The last clinical investigation in this comparative phase will be performed at week 16. The physical examination will be equal with the one performed in the screening phase. The patients must perform a new diet registration during the following 4 days and undergo the second DXA investigation for measurements of BMD. Additionally, the patients will record their change in concomitant medication. Blood samples will be collected for measurements of Osteocalcin, vitamin K2, BTMs, HbA1C, Lipids and other hematological and biochemical variables. Patients with a T-score < -2.5 based on the DXA investigation will be classified as Osteoporotic and withdrawn from the study. If possible and

in accordance with the responsible investigator, the patient will be given Antiresorptive treatment in addition to OED of Jarlsberg cheese and vitamin D + Ca.

The patients randomized to only vitamin D + Ca (Controls) at baseline will now receive OED of Jarlsberg cheese equal with the other patients and continue in the follow-up phase of the study. Cheese for the next 4 weeks will be delivered together with compliance & activity form.

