#### *6.2.4: End of study*

The end of the study will be Week 32 for the patients allocated to Jarlsberg cheese at baseline and Week 48 for those allocated to vitamin D + Ca at baseline. At the end of the study, the “End-of-treatment” Case Record Form (CRF) must be filled in by the investigator.

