#### *6.2.5: One year follow-up*

The patient finalizing the study will be asked if they want to continue with daily OED of Jarlsberg cheese. They will receive the cheese free of charge but must meet for a new investigation one year later. This investigation will consist of a physical examination, and a DXA measurement. A new blood sample will be taken for measurement of Osteocalcin, BTMs, vitamin K2, lipids and HbA1C. Additionally, the number of bone fractures during the last year will be recorded.

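### Aim 3 asks for a time-to-treatment comparison with and without Jarlsberg, but the schedule gives only one with/without reading, at the week-16 DXA

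*Protocol*

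**What the plan says.** Aim 3, in both 1.3 and 2.4, is "To compare daily intake of Calcium (Ca) and vitamin D with and without OED of Jarlsberg on Time-to-Osteoporotic (TTO) treatment is recommended".

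The schedule that has to deliver it is fixed in the protocol:

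- 5.1: "DXA will be used as a surrogate measurement of BMD at baseline and every 16 weeks".
- 6.2.2: "The last clinical investigation in this comparative phase will be performed at week 16". The second DXA belongs to this visit.
- 4.1: "At week 16, the patients in the control-group will be switched to additional daily OED of Jarlsberg cheese for 32 weeks".
- 6.2.4: "The end of the study will be Week 32 for the patients allocated to Jarlsberg cheese at baseline and Week 48 for those allocated" to the supplements alone.
- 6.2.5, on patients who choose to go on eating the cheese after the study: "They will receive the cheese free of charge but must meet for a new investigation one year later".

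The event is tied to the T-score. Section 1.8.2 says that patients at or below -2.5 "will discontinue the study and switched to antiresorptive treatment plus daily OED of Jarlsberg cheese". Section 4.1 puts the limit differently: "Patient with T-score < -2.5 classifies as Osteoporotic patients will be withdrawn from the study". Sections 6.2.2 and 6.2.3 repeat the strict form, and 5.1 defines osteoporosis as below -2.5. Eligibility (1.4, 3.2.1) requires a T-score larger than -2.5.

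**The concern.** A comparison of times to an event needs follow-up in both conditions over a period in which event times can differ. Here the without-Jarlsberg condition lasts 16 weeks, and the instrument that detects the event is read once in that period, at its end. The aim therefore names a quantity that the design does not observe under randomisation.

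What is at stake is interpretation. If times to treatment are compared over the whole study and reported in the words of Aim 3, any difference arising after week 16 would be presented as an effect of having cheese versus not having it. In fact both groups are then eating it. Section 12.7 says the results will be used for marketing, so the wording of the claim matters.

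**Working it through.** **Step 1. Set the DXA schedule beside the treatment received** (5.1, 4.1, 6.2.4, 6.2.5 and the flow chart in 1.11, which indexes the control visits as 16(0), 32(16) and 48(32)).

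| DXA | Jarlsberg group, weeks on cheese | Control group, weeks on cheese | What a comparison by initial allocation shows |
|---|---|---|---|
| Baseline | 0 | 0 | starting point |
| Week 16 | 16 | 0 | with v without Jarlsberg |
| Week 32 | 32 | 16 | early v delayed start |
| Week 48 | none (study ended at week 32) | 32 | no comparison |
| One year after last visit | continuing on cheese | continuing on cheese | no without-cheese time |

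Of the two post-baseline DXAs shared by both groups, one falls while the treatments differ.

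**Step 2. Possible event times.** An event is recorded when a DXA shows the T-score limit. In the with/without period the first and only such DXA is at week 16. The recorded time can take one value, so the data reduce to one 2x2 table: event or no event at week 16, by group. No analysis method can add randomised off-cheese time after that visit. A model with cheese as a time-varying exposure is possible, but it rests on assumptions rather than on randomisation.

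**Step 3. What the sample size covers.** The protocol's only figures are 24 finishers and 30 enrolled per group, for a BMD difference of 1 SD (1.9, 11.3). With n = 2(z_alpha/2 + z_power)^2 and two-sided 5%:

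- 90% power: 2(1.960 + 1.282)^2 = 21.0, rounded up to 22.
- 95% power: 2(1.960 + 1.645)^2 = 26.0, so 26.

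The stated 24 lies between these, and 24 x 1.25 = 30. These figures concern BMD. No event rate or sample size is given for Aim 3.

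**Step 4. Scale of the week-16 table.** The event rates here are assumptions. Power is the sum over all (a, b) of Bin(a; n, r) x Bin(b; n, s) for the tables with two-sided p <= 0.05. Here r is the control risk and s the risk on cheese. Expected control events are n x r: 1.2, 2.4, 3.6 and 4.8 at n = 24, and 1.5, 3.0, 4.5 and 6.0 at n = 30, for r = 5, 10, 15 and 20%.

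| Assumed effect | r | Fisher / uncorrected chi-square, n = 24 | Fisher / uncorrected chi-square, n = 30 |
|---|---|---|---|
| s = r/2 | 5% | 0.3% / 1.7% | 0.2% / 3.1% |
| s = r/2 | 10% | 2.8% / 7.6% | 1.9% / 10.6% |
| s = r/2 | 15% | 6.4% / 12.7% | 5.3% / 15.7% |
| s = r/2 | 20% | 9.7% / 16.7% | 9.6% / 19.4% |
| 1-SD shift, s = 1.1% | 10% | 6.6% / 17% | 5.4% / 27% |
| 1-SD shift, s = 2.1% | 15% | 19% / 34% | 18% / 47% |
| 1-SD shift, s = 3.3% | 20% | 32% / 47% | 33% / 59% |
| s = 0 | 20% | 54% / 74% | 57% / 88% |

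The 1-SD rows take s = Phi(Phi^-1(r) - 1), that is, a normal T-score shifted by one SD. Power depends heavily on the assumed effect.

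**Step 5. Precision, by example.** With 4 v 2 events, the Newcombe 95% interval for the difference is:

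- 24 per group: 8.3 points (-11.8 to 28.4).
- 30 per group: 6.7 points (-10.0 to 23.7).

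**Step 6. The limit.** A T-score of exactly -2.5 is an event under 1.8.2 and not under 4.1, 5.1, 6.2.2 or 6.2.3. The same value is ineligible at entry.

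**The case against.** The aim says compare; it does not say that the comparison must be a randomised with/without contrast throughout. The design is openly called semi-crossover. Time to the T-score limit over weeks 16 and 32, by initial allocation, is a valid test of no cheese effect, because the groups are still those formed by randomisation. **This stands.** A reader might infer that everything after week 16 is useless or no longer randomised, and the documents do not support that. Week 32 is a sound comparison of early with delayed start. It is not the comparison that Aim 3 words.

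A reader might also infer that the week-16 proportion has hopeless power and can only be descriptive. That does not hold in general. Power stays under 20% if cheese halves the risk, but the protocol plans on a much larger effect (1 SD of BMD, with little or no gain expected on supplements alone, 11.3). Under stronger assumed effects power reaches 59% or even 88%. The trial was not sized for this aim, and the point does not depend on power.

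The event in the aim is treatment being recommended, and 6.2.2 and 6.2.3 make antiresorptive treatment subject to the investigator's agreement. The operational definition, and any survival method, may be in a statistical analysis plan that is not at hand, so their absence is not held against the protocol. But the T-score at DXA is the only trigger stated, and no analysis plan can create off-cheese follow-up after week 16.

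The conflict over the T-score limit is a separate matter. It has no bearing on whether a time contrast exists.

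**Conclusion.** The point holds as a mismatch between Aim 3 and the visit schedule. One post-baseline DXA falls while the groups differ in having or not having Jarlsberg, so the randomised with/without contrast is a proportion at week 16. The week-32 comparison is valid but answers early versus delayed start, and nothing later contributes randomised without-cheese time. This rests on the schedule in 4.1, 5.1, 6.2.2 and 6.2.4 and on the T-score at DXA being the only stated trigger. It needs no assumption about event rates, and no general claim about power is made.

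The consequence is limited to the third aim. Time to treatment is not among the main variables in 1.7 and is not the basis of the sample size. A reader might infer that the switch also undermines the BMD comparison. It does not, because the week-16 BMD reading comes at the end of the parallel period.

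The inconsistent limit is a minor point and affects only patients at exactly -2.5.

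**What to change.** - In 1.3 and 2.4, restate Aim 3 as the proportion of patients reaching the osteoporosis T-score limit at the week-16 DXA, by group, with a confidence interval for the difference.
- Add one sentence on later data. Any comparison by initial allocation through week 32 is reported as early versus delayed start. Week-48 and one-year DXA results are reported within group by weeks on cheese, as the flow chart already indexes the control visits.
- Separately, use at or below -2.5 throughout by changing 4.1, 5.1, 6.2.2 and 6.2.3 to match 1.8.2. This fits the existing eligibility bound in 1.4 and 3.2.1, so eligibility does not change.

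The cost is the with/without time-to-event claim, which is given up. The rest is wording, with no new visits, measurements or patients.
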